11.5. Other Assessments

11.5.1. Confirmation of histological diagnosis

Histological confirmation of diagnosis of thymic carcinoma for all patients will be obtained by an Independent Review Committee during the course of the study, based on paraffin embedded tumor tissue slides retrieved from patients.

11.5.2. Pharmacokinetics

No blood sampling is expected during the study for pharmacokinetics analysis. Blood samples may be collected if, in the opinion of the Investigator and of the Sponsor, an evaluation of the systemic exposure of PHA-848125AC is needed for safety reasons. In such case the IRB will be notified.

If applicable, the actual time of sample collection has to be recorded in the Case Report Form.

11.5.3. Laboratory Exploratory Studies on Tumor Specimens

11.5.3.1. Collection of Tumor Specimen(s)

Paraffin-embedded tissue blocks or derived slides containing the original diagnostic tumor samples from consenting patients will be procured from the institutions where the diagnostic procedures were performed.

Tumor blocks or derived slides will be shipped by a commercial courier under controlled temperature conditions in protective packaging.

11.5.3.2. Molecular characterization of patient's tumors

Molecular analysis of p53, p21, p27, cyclin D1, p75, TRKA and other genes/proteins involved in the PHA-848125AC mechanism of action on paraffin-embedded tissues of consenting patients will be performed in designated facilities in NMS and NIH/NCI.

12. STATISTICAL METHODS

12.1. Sample Size Calculation

In consideration of the exploratory nature of the study, the Simon's optimal 2-stage design [42] is adopted for this single-arm, open-label, multicentre phase II clinical trial.

The total number of evaluable patients for the primary efficacy analysis ranges from 17 (if the trial stops at the end of the 1st step) to 54 (if the trial proceeds up to the completion of the 2^{nd} step). Accounting for a 10%-15% proportion of non evaluable patients, up to 20

Tiziana Life Sciences, PLC - Confidential Page 74 of 101

Milciclib maleate (PHA-848125AC)	CDKO-125a-006-P4
Protocol for Study CDKO-125a-006	09 March 2017

patients could be required in the 1st stage of the study and up to 60 patients could be required for completing the trial (1st and 2nd stage).

The primary endpoint of the study is the progression-free survival status at 3 months and the primary efficacy analysis will be performed on the proportion of successes (i.e. patients alive and in a progression-free status at 3 months since treatment start) out of the total number of evaluable patients (PFS-3 rate).

Considering a 33% PFS-3 rate as clinically interesting, against a clinically uninteresting hypothesis of a PFS-3 rate no higher than 17%, the system of hypotheses to be tested is:

*H*₀: $p \le p_0$, $p_0 = 0.17$ vs. *H*₁: $p \ge p_1$, $p_1 = 0.33$

The analysis will be performed at the overall level $\alpha = 0.05$ (1-sided). The design below outlined will provide 80% power (1- β) not to reject the treatment as insufficiently effective, if the true PFS-3 rate is 33% or higher.

In the first stage, 17 evaluable patients are to be assessed. If \leq 3 successes are observed, the study treatment will be considered as providing insufficient evidence of efficacy and the trial will be terminated.

If at least 4 successes are observed in the 1st stage, patients' enrollment will proceed up to an overall enrollment of 54 evaluable patients. At the final analysis, \geq 14/54 successes (PFS-3 rate \geq 25.9%) will be required to reject the null hypothesis and suggest that the drug might have an interesting level of efficacy. The progression free survival at 3 months will be evaluated based on the antitumor activity evaluated during the oncologic assessment at 3 months after first drug administration. The oncologic assessment will be performed preferably between 92-98 days from treatment start, but all patients with assessments performed up to 134 days will be considered evaluable for the primary end-point.

		nowow	1 st Stage (*)		2 nd Stage		
H_0 vs. H_1	a (1-sided)	power (1-β)	Pts	STOP and Reject drug	Pts	Reject drug	Do not reject drug
$p_0 \le 0.17 \text{ vs. } p_1 \ge 0.33$ (PFS-3 rate)	0.05	0.80	17 evaluable pts	$\leq 3 / 17$ successes	54 evaluable pts	≤ 13 / 54 succ. (PFS-3 rate ≤24.1%)	\geq 14 / 54 succ. (PFS-3 rate \geq 25.9%)
(*) Probability of Early Termination: PET=0.675, if the drug is actually ineffective; Probability to continue the trial > 0.863, if the true PFS-3 rate is at least 33%:							
Expected sample size assuming ineffective drug: 29							
No. of enrolled patients: ≤20 patients in the 1st stage, ≤60 patients overall (if 10%-15% inevaluable patients)							

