Baseline characterization of selected biomarkers (p53, p21, p27, cyclin D1, p75, TRKA and other genes/proteins involved in the PHA-848125AC mechanism of action) in tumor tissue of consenting patients. Assessments will be done on paraffin embedded blocks, obtained from all patients before study entry, by IHC and other possible techniques, such as FISH and PCR.

Study Design

In consideration of the exploratory nature of the study, the Simon's optimal 2 stage design [23] is adopted for this single-arm, open-label, multicentre phase II clinical trial.

Histological confirmation of diagnosis of thymic carcinoma for all patients will be obtained by an Independent Review Committee.

Sample Size Determination and Statistical Methods:

The total number of evaluable patients for the primary efficacy analysis ranges from 17 (if the trial stops at the end of the 1^{st} stage) to 54 (if the trial proceeds up to the completion of the 2^{nd} stage). Accounting for a 10%-15% proportion of non evaluable patients, up to 20 patients could be required in the 1^{st} stage of the study and up to overall 60 patients could be required for completing the trial (1^{st} and 2^{nd} stage).

The primary endpoint of the study is the progression-free survival status at 3 months and the primary efficacy analysis will be performed on the proportion of successes (i.e. patients alive and in a progression-free status at 3 months since treatment start) out of the total number of evaluable patients (PFS-3 rate).

Considering a 33% PFS-3 rate as clinically interesting, against a clinically uninteresting hypothesis of a PFS-3 rate no higher than 17%, the system of hypotheses to be tested is:

Name of Finished Product: PHA-848125AC (Milciclib maleate)

 $H_0: p \le p_0, p_0 = 0.17$ vs. $H_1: p \ge p_1, p_1 = 0.33$

The analysis will be performed at the overall level $\alpha = 0.05$ (1-sided). The design below outlined will provide 80% power (1- β) not to reject the treatment as insufficiently effective, if the true PFS-3 rate is 33% or higher.

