In the first stage, 17 evaluable patients are to be assessed. If ≤ 3 successes are observed, the study treatment will be considered as providing insufficient evidence of efficacy and the trial will be terminated. If at least 4 successes are observed in the 1st stage, patients' enrollment will proceed up to an overall enrollment of 54 evaluable patients. At the final analysis, $\geq 14/54$ successes (PFS-3 rate $\geq 25.9\%$) will be required to reject the null hypothesis and suggest that the drug might have an interesting level of efficacy.

			1 st Stage (*)		2 nd Stage			
H ₀ vs. H ₁	α (1- sided)	powe r (1- β)	Pts	STOP and reject drug	Pts	Reject drug	Do not reject drug	
$p_0 \le 0.17 \ vs. \ p_1 \ge 0.33 \ (PFS-3 \ rate)$	0.05	0.80	17 evaluable pts	≤ 3 / 17 successes	54 evaluable pts	≤ 13 / 54 succ. (PFS-3 rate ≤ 24.1%)	≥ 14 / 54 succ. (PFS-3 rate ≥ 25.9%)	
(*) Probability of Early Termination: PET=0.675, if the drug is actually ineffective; Probability to continue the trial > 0.863, if the true PFS-3 rate is at least 33%:								
Expected sample size assuming ineffective drug: 29								
No. of enrolled patients: ≤ 20 patients in the 1 st stage, ≤ 60 patients overall (if 10%-15% inevaluable patients)								

The progression free survival at 3 months will be evaluated based on the antitumor activity evaluated during the oncologic assessment at 3 months after first drug administration. The oncologic assessment will be performed preferably between 92-98 days from treatment start, but all patients with assessments performed up to 134 days will be considered evaluable for the primary end-point.

Supportive analyses of the primary endpoint will include the estimation of the PFS-3 rate together with its exact, two-tail, 95% confidence interval and the estimation of the PFS curve by the Kaplan-Meier method [24] in both the evaluable and the treated patient population. The other efficacy endpoints including the confirmed objective response rate, the disease control rate, the duration of response, and the overall survival will be descriptively analyzed in both the evaluable and the treated patient populations. Kaplan-Meier estimates will be generated and plotted for the overall survival endpoint.

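### The overall enrolment ceiling of 60 is stated for 10%-15% non-evaluable patients but covers only 10%; 15% needs 64

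*Protocol*

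**What the plan says.** Section 12.1 fixes the design in evaluable patients. In the first stage "17 evaluable patients are to be assessed"; if at least 4 succeed, "patients' enrollment will proceed up to an overall enrollment of 54 evaluable patients". At the end, at least 14 successes out of 54 are required. The stated one-sided level is 0.05 and the stated power is 80%, for PFS-3 rates of 17% against 33%.

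The same section then turns evaluable numbers into enrolled numbers. The text reads "Accounting for a 10%-15% proportion of non evaluable patients, up to 20" patients for the first stage, and for the whole trial says that "up to 60 patients could be required for completing the trial". The last row of the design table attaches the range directly to the overall figure: "≤60 patients overall (if 10%-15% inevaluable patients").

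The same figures stand in Section 5 and in the synopsis, where the text says that "up to overall 60 patients could be required for completing the trial" and the table repeats "patients overall (if 10%-15% inevaluable patients"). The figure therefore appears in five places, always with the same range.

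**The concern.** An upper limit given for a range should hold at the unfavourable end of that range. The stage 1 limit does and the overall limit does not, so the two limits rest on different assumptions although the protocol presents them as resting on one.

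The enrolled number is what sites, ethics committees and drug supply work from. If the non-evaluable proportion exceeds 10%, which the protocol itself anticipates, one of two things is to be expected: enrolment passes the stated limit, or the trial ends with fewer than the 54 evaluable patients on which the stated power depends. The protocol does not say which of the two gives way.

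**Working it through.** **Inputs, all from Section 12.1:** 17 evaluable in stage 1; 54 evaluable overall; non-evaluable proportion *d* from 10% to 15%; stated ceilings 20 and 60; p0 = 0.17, p1 = 0.33; stop if 3 or fewer successes in 17; reject the null hypothesis at 14 or more in total.

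**Step 1. Reproduce the design.** An exact binomial calculation for 17 and 54 evaluable gives a probability of early termination under p0 of 0.675, a probability of continuing under p1 of 0.863, and an expected sample size under p0 of 17 + 37 × (1 − 0.675) = 29.0. Type I error is 0.0496 and power 0.806. All agree with the protocol, so the evaluable sample size and the boundaries are sound.

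**Step 2. Inflate for non-evaluable patients.** Enrolled = evaluable / (1 − *d*), rounded up.

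| *d* | Stage 1 (17 evaluable) | Overall (54 evaluable) |
|---|---|---|
| 10% | 17/0.90 = 18.9, so 19 | 54/0.90 = 60.0, so **60** |
| 12.5% | 17/0.875 = 19.4, so 20 | 54/0.875 = 61.7, so 62 |
| 15% | 17/0.85 = 20.0, so **20** | 54/0.85 = 63.5, so 64 |

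The bold cells are the protocol's figures. The stage 1 ceiling is exact at 15% and the overall ceiling exact at 10%. The cruder inflation 54 × 1.15 = 62.1, so 63, does not give 60 at 15% either. Inflating by stage at 15% gives 20 + 37/0.85 = 20 + 43.5, so 20 + 44 = 64, the same answer as the overall calculation.

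**Step 3. Set the two ceilings together.** If stage 1 uses its full 20, a limit of 60 leaves 60 − 20 = 40 enrolments for the remaining 54 − 17 = 37 evaluable patients. That allows 1 − 37/40 = 7.5% non-evaluable in stage 2, below the stated range.

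**Step 4. What 60 enrolled would yield.** Expected evaluable: 60 × 0.90 = 54, 60 × 0.875 = 52.5, 60 × 0.85 = 51. If patients become non-evaluable independently of one another, the chance that 60 enrolled give at least 54 evaluable is 0.61 at 10%, 0.36 at 12.5% and 0.18 at 15%.

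**Step 5. Operating characteristics if 60 were a hard cap.** Stage 1 rule unchanged, at least 14 successes still required:

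| Evaluable | Type I error (p = 0.17) | Power (p = 0.33) |
|---|---|---|
| 54 | 0.0496 | 0.806 |
| 53 | 0.044 | 0.794 |
| 52 | 0.039 | 0.781 |
| 51 | 0.034 | 0.766 |

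Power is below 80% as soon as one evaluable patient is missing. Lowering the requirement to 13 at 51 evaluable would restore power to 0.812 but raise type I error to 0.062, so the requirement of 14 cannot be relaxed within the 0.05 level.

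**The case against.** The strongest reply is that the rule that governs enrolment is written in evaluable patients: "enrollment will proceed up to an overall enrollment of 54 evaluable patients". The 60 is described as a number that could be required, which is planning language, and nothing says that recruitment stops there. On that reading power and type I error are exactly as stated. This stands, and it is why the power loss in Step 5 is conditional. It does not make 60 right for 15%.

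A second reply is that the authors may have meant 15% for the small first stage and 10% overall, and summarised this as a range. Both figures then reproduce exactly. But the table attaches the whole range to the overall figure, so the wording would still need correcting.

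Third, the 7.5% in Step 3 subtracts a 15% figure from a 10% figure. At a uniform 10%, stage 1 needs 19, leaving 41 for 37 evaluable, or 9.8% non-evaluable. That is fair: Step 3 shows the mixing of the two ends and is not a second error.

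Fourth, 64 is also only an expected-value inflation. With 64 enrolled at 15% non-evaluable, the chance of at least 54 evaluable is about 0.64, much like the 0.61 for 60 at 10%. The correction follows the protocol's own convention and carries the same limitation.

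Finally, this version is dated 09 March 2017 and sets a data cut-off of 31 May 2017, 83 days later, while the 3-month scan is due on days 92-98. Patients first treated under this version could not have that scan in its scheduled window by the cut-off, so the practical effect now may be small. The protocol does not say whether enrolment is closed, and the figure in the current text is still wrong.

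**Conclusion.** The concern holds. For the protocol's own range, the overall enrolment figure should run from 60 to 64; the single figure of 60 covers the 10% end only, while the stage 1 figure of 20 covers the 15% end. The shortfall is 2 patients at 12.5% and 4 at 15%.

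The consequence is modest. The number of evaluable patients, the decision boundaries, the type I error and the stated power are correct. If enrolment continues to 54 evaluable, only the stated ceiling is exceeded. A power loss, to about 0.77 at 15% non-evaluable, arises only on three assumptions that the protocol does not state: that 60 is a hard stop, that the expected 51 evaluable are obtained, and that at least 14 successes are still required. Type I error is not inflated in that case.

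The error is definite, repeated and cheap to correct, so it should be corrected.

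**What to change.** In Section 12.1 (text and table), Section 5 and the synopsis (text and table), replace the single overall figure by up to 60 enrolled at 10% and up to 64 at 15% non-evaluable. Alternatively, keep 60, state that it covers 10% only, and add that power is about 77% if 15% are non-evaluable and enrolment stops at 60.

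The stage 1 figure of 20, the 54 evaluable patients and the requirement of at least 14 successes stay as they are. The cost is one corrected figure in five places, with no change to the design or the analysis. If the first option is taken and enrolment is still open, up to 4 more patients may need to be provided for.

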12.2. Definition of Analyzed Study Populations

For the purpose of the analysis, the following patient populations are defined and the endpoints, to be analyzed in these populations, are specified:

- *Screened Patients:* This population will include all subjects who are screened about their eligibility for the trial, regardless of whether or not they will be enrolled in the study. This population will be evaluated in the analysis of patients' disposition.
- *Enrolled Patients:* This population will include all subjects who are enrolled in the trial, regardless of whether subjects receive the study drug or not. This population will be evaluated in the analysis of patients' disposition.
- *Treated Patients:* The treated patient population consists of all enrolled patients who actually receive at least one study drug administration. This population will be evaluated in the analysis of patient disposition, baseline characteristics, treatment efficacy and safety and treatment exposure.
- *Patients Evaluable for Efficacy Analysis:* This is the patient population for the primary efficacy analysis of PFS-3 rate and consists of all treated patients who fulfill the following additional conditions:
 - They have received histological confirmation of thymic carcinoma by an Independent Review Committee
 - They receive at least 80% of drug in the first two cycles overall.
 - They have baseline and ≥1 on-treatment tumor/oncologic assessment(s) or die before tumor re-assessment.

If deemed of clinical interest, patient disposition, baseline characteristics, treatment efficacy and safety and treatment exposure will be analyzed also in this population.

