Patients' baseline characteristics, treatment exposure and safety data will be analyzed in the treated patient population and, if clinically interesting, in other subsets such as the evaluable patient population. Descriptive statistical analyses and individual data listings will be used to report all collected data including patient disposition, protocol deviations, baseline characteristics, treatment exposure, efficacy, and safety data.

Patient Populations:

• *Screened Patients:* This population will include all subjects who are screened about their eligibility for the trial, regardless of whether or not they will be enrolled in the study. This population will be

Tiziana Life Sciences, PLC - Confidential Page 12 of 101

Name of Finished Product: PHA-848125AC (Milciclib maleate)

evaluated in the analysis of patients' disposition.

- *Enrolled Patients:* This population will include all subjects who are enrolled in the trial, regardless of whether subjects receive the study drug or not. This population will be evaluated in the analysis of patients' disposition.
- *Treated Patients:* The treated patient population consists of all enrolled patients who actually receive at least one study drug administration. This population will be evaluated in the analysis of patient disposition, baseline characteristics, treatment efficacy and safety and treatment exposure.
- *Patients Evaluable for Efficacy Analysis:* This is the patient population for the primary efficacy analysis of PFS-3 rate and consists of all treated patients who fulfill the following additional conditions:
 - They have received histological confirmation of thymic carcinoma by an Independent Review Committee
 - They have received at least 80% of drug in the first two cycles overall.
 - They have baseline and ≥1 on-treatment tumor/oncologic assessment(s) or die before tumor re-assessment.

If deemed of clinical interest, patient disposition, baseline characteristics, treatment efficacy and safety and treatment exposure will be analyzed also in this population.

Exploratory studies

Exploratory analyses on the relationship of molecular features of p53, p21, p27, cyclin D1, p75, TRKA and other genes/proteins involved in the PHA-848125AC mechanism of action with treatment efficacy variables will be performed if sufficient data and samples (tumor biopsies obtained before study entry) are collected.

Subject Selection

Subject Inclusion Criteria

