10. SUBJECT WITHDRAWAL FROM STUDY PARTICIPATION

Patients may continue with therapy unless any of the following occurs:

- Disease progression at any time
- Unacceptable toxicity dictating cessation of treatment
- Changing in medical status of the patient (including pregnancy) such that the Investigator believes that patient safety will be compromised or that it would be in the best interest of the patient to stop treatment
- Withdrawal of consent (includes any reason why the patient decides to discontinue completely his/her study participation and does not wish that the Sponsor follows him/her to collect information regarding disease status. In this case no further evaluation should be performed and no attempts should be made to collect additional data)
- Patient's refusal to continue the study treatment (includes any patient who does not want to be treated anymore in the frame of this study but accepts that the Sponsor continues to follow him/her in order to collect information regarding disease status). Applicable only for patients treated pre-Amendment 4.
- Non-compliance by the patient with protocol requirements. Applicable only for patients treated pre-Amendment 4.
- Patient lost to follow up. If a patient does not return for a scheduled visit, every effort should be made to contact the patient. In any circumstance, every effort should be made to document patient outcome. Applicable only for patients treated pre-Amendment 4.

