11.2.1. Tumor Imaging

Tumor imaging by chest/abdomen/pelvic CT scan or MRI: the baseline tumor assessment by CT scan or MRI has to be performed within 3 weeks prior to the treatment start; during the treatment period (irrespectively of cycles duration) the first assessments will be performed 6 weeks (between days 42 and 48) after first drug administration, **the second one 3 months (between days 92 and 98) after first drug administration**, the following ones every 6 weeks (between days 42 and 48) after the previous one (or whenever a clinical

> Tiziana Life Sciences, PLC - Confidential Page 58 of 101

Milciclib maleate (PHA-848125AC)	CDKO-125a-006-P4
Protocol for Study CDKO-125a-006	09 March 2017

deterioration will be observed) and at end of last cycle (if not done in the previous 4 weeks). For patients with responding tumors (complete or partial response), response confirmation must be performed no less than 4 weeks after the criteria for response are first met.

In addition, in patients withdrawn from study treatment for causes other than disease progression, tumor response will have to be reassessed at the time of study drug discontinuation, unless a tumor assessment was performed within the previous 4 weeks. In these patients, regular tumor imaging assessments are to be performed every 6 weeks during follow-up, until PD or until a new antitumor therapy starts.

The same method and technique (CT scan, spiral CT scan or MRI) should be used to characterize each identified and reported lesion at baseline and during follow-up. Imaging-based evaluation, over clinical examination, is the required technique when both could be used to assess the antitumor effect of the treatment.

CT scan is the desirable method for lesion measurement. CT scans should have a maximum slices thickness of 5 mm and a minimum size for a measurable lesion is twice that: 10 mm (even if slice thickness is <5 mm). If scanners with slice thickness > 5 mm are used, to qualify for a measurable lesion, the minimum lesion size must have a longest diameter twice the actual slice thickness. MRI is acceptable (but not for lung lesions), provided that the size of the measurable lesion is twice the slice thickness of the MRI.

All patients' files and scans must be available for source verification.

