12.3.4. Efficacy Analyses

Primary Efficacy Endpoint

For the primary efficacy analysis, the primary endpoint, *i.e.* the PFS-3 rate, will be calculated as the proportion of evaluable patients (see Section 12.2) known to be alive and progression-free at \geq 3 months since study treatment start out of the total number of evaluable patients (see Section 4.2.1). Decision rules will be applied in the primary efficacy analysis as described in Section 12.1, i.e.:

- At least 4 / 17 evaluable patients alive and progression free at \ge 3 months are required not to early terminate the trial and reject the drug at the end of the first step.
- At least 14 / 54 evaluable patients alive and progression free at \geq 3 months are required at the end of the second step to reject the null hypothesis of a PFS-3 rate as low as 17%, at the 1-sided α -level of 0.05.

Supportive analyses of the primary endpoint will include the estimation of the PFS-3 rate together with its exact, two-tail, 95% confidence interval and the estimation of the PFS curve by the Kaplan-Meier method [43] in both the evaluable and the treated patient population.

Other Efficacy Endpoints

The secondary efficacy endpoints outlined in section 4.2.2 and including the confirmed objective response rate, the disease control rate, the duration of response and the overall survival will be analyzed in both the evaluable and the treated patient population as follows:

Objective tumor response rate: Point and 95% confidence interval estimates will be calculated for the objective tumor response rate (confirmed CRs or PRs). The analysis will

Tiziana Life Sciences, PLC - Confidential Page 77 of 101 be performed in the evaluable and in the treated patient populations. The estimates of the rates of unconfirmed tumor objective responses will also be provided and considered as supportive.

Disease control rate: Point and 95% confidence interval estimates will be calculated for the disease control rate (confirmed CRs / PRs and SD \ge 6 weeks). The analysis will be performed in the evaluable and in the treated patient populations.

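### The primary PFS-3 set requires 80% of the drug over two cycles with no exception, so patients who die or stop for progression before about day 19 leave the denominator of both decision rules

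*Protocol*

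**What the plan says.** Protocol 12.2 defines the primary efficacy set as treated patients who meet three conditions together. The first is confirmation of thymic carcinoma by the independent committee. The second is "They receive at least 80% of drug in the first two cycles overall". The third is "They have baseline and ≥1 on-treatment tumor/oncologic assessment(s) or die before tumor re-assessment". The synopsis repeats the second as "They have received at least 80% of drug in the first two cycles overall". Only the third condition makes allowance for death; the second makes none for death, progression or any other reason for stopping.

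Section 10 lists "Disease progression at any time" among the events that end therapy. Section 12.1 counts accrual in evaluable patients: 17 in stage 1, and after at least 4 successes "enrollment will proceed up to an overall enrollment of 54 evaluable patients". It foresees up to 20 patients in stage 1 and 60 overall, on 10%-15% non-evaluable. Section 12.3.4 applies 4/17 and 14/54 to evaluable patients. It adds: "Supportive analyses of the primary endpoint will include the estimation of the PFS-3 rate together with its exact, two-tail, 95% confidence interval", in both the evaluable and the treated populations.

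**The concern.** A single-arm test against a fixed rate is only as sound as its denominator. Here entry to the denominator depends on how much drug a patient took in the first weeks, and an early death or progression is one reason for taking less. Such a patient is a failure for PFS-3, but under the 80% condition drops out of the calculation, and enrolment continues until another patient fills the place.

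The second and third conditions also sit badly together. A patient who dies on day 12 meets the third condition through its death clause and still fails the second.

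At stake are the futility stop after 17 patients and the final claim of activity after 54. The design has almost no slack in type I error, so a small shift in the success rate among evaluable patients takes it above 5%.

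**Working it through.** **Inputs.** From 12.1: p0 = 0.17, p1 = 0.33; stop at 3 or fewer successes in 17; reject the null at 14 or more in 54. From 9.4.1: dosing on days 1-7 of each 14-day cycle. The share of patients removed is not in the protocol and is assumed.

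**The plan's own figures.** With X1 ~ Bin(17, p) and X2 ~ Bin(37, p):

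- early stop = P(X1 ≤ 3)
- P(reject) = sum over x from 4 to 17 of P(X1 = x) × P(X2 ≥ 14 − x)

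At p = 0.17 the early stop is 0.675 and type I error 0.0496. At p = 0.33 power is 0.806. These agree with the stated 0.675, 0.05 and 0.80.

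**When 80% is reached.** Two cycles give 14 planned doses, on days 1-7 and 15-21. 0.80 × 14 = 11.2. Eleven doses are 78.6% and fail; twelve are 85.7% and pass. At full dose without delay the 12th dose falls on day 19.

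**Effect on type I error.** Suppose 17% describes all confirmed patients from treatment start, a share e is removed, and those removed would succeed at rate s. The rate among those left is p = (0.17 − s·e)/(1 − e).

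| e | s = 0: p | early stop | type I error | s = 0.085: type I error | s = 0.17: type I error |
|---|---|---|---|---|---|
| 0 | 0.1700 | 0.675 | 0.0496 | 0.0496 | 0.0496 |
| 2% | 0.1735 | 0.660 | 0.057 | 0.053 | 0.0496 |
| 5% | 0.1789 | 0.638 | 0.070 | 0.059 | 0.0496 |
| 10% | 0.1889 | 0.596 | 0.100 | 0.072 | 0.0496 |

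One certain failure removed alongside 54 evaluable patients gives p = 0.17 × 55/54 = 0.1731 and type I error 0.056.

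The 10% row is an upper end, not a forecast. With 60 enrolled and 54 evaluable, (60 − 54)/60 = 10% covers every reason for non-evaluability. Some of that will be histology, since 6.1 admits B3 thymoma and only confirmed thymic carcinoma is evaluable.

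**Power if the removed patients are counted.** If 33% was meant for the present set and a share e of extra failures enters, p = 0.33 × (1 − e). With 14/54, power goes from 0.806 to 0.783 (2%), 0.744 (5%) and 0.669 (10%).

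**Final cut-off if the number analysed is not 54** (stage 1 kept at 4/17):

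| n | successes needed | type I error | power at 0.33 |
|---|---|---|---|
| 57 | 14 | 0.068 | 0.831 |
| 60 | 14 | 0.089 | 0.845 |
| 55 | 15 | 0.031 | 0.774 |
| 57 | 15 | 0.039 | 0.800 |
| 59 | 15 | 0.0495 | 0.819 |
| 60 | 15 | 0.055 | 0.826 |
| 60 | 16 | 0.031 | 0.794 |

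**The case against.** Five points can fairly be made for the plan.

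1. **The hypothesis is stated for evaluable patients.** If 17% and 33% describe that set, the stated 5% is correct. This stands. The 17% rests on a median of 5.1 weeks in a pemetrexed study that 3.1 reports in evaluable patients, without defining the term. A reader might infer that the protocol's error rate is wrong; the document does not show that.

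2. **Few patients will be affected.** Entry requires ECOG 0-1 and an expected survival of at least 3 months, and the first scheduled scan is at days 42-48. This also stands. A reader might describe the set as patients who survived progression-free through most of two cycles. That goes too far: someone with silent early progression who takes the doses stays in and counts as a failure. A reader might also fit an exponential curve to the 5.1-week median, which puts about 29.5% of failures before day 19. That is no estimate of the share removed, because most such progression would not be detected, or stop treatment, that early.

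3. **The death clause still does some work.** It covers deaths from about day 19 to the first scan. It therefore does not prove that earlier deaths were meant to count, only that the two conditions pull in different directions.

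4. **The denominator of the 80% is not stated.** If it meant drug due while on treatment, a compliant patient who died on day 10 would qualify. Planned doses over the first two cycles is the more natural reading, but 12.2 does not settle it.

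5. **PFS-3 is also estimated in treated patients.** The effect will therefore be visible. That analysis is supportive, however, and neither decision rule uses it.

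The exclusion is also not wholly one-sided. Patients who stop early for toxicity are removed too, and some of them may be progression-free at 3 months.

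**Conclusion.** The point holds as a defect in the definition of the primary set. On the natural reading of the 80% condition, a treated patient with confirmed histology who dies, or stops for progression or deterioration, before day 19 at the earliest is dropped and in effect replaced. The direction is likely to favour the drug, and the selection acts on both 4/17 and 14/54.

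The size is unknown and probably small. A rise in type I error from 0.0496 to between 0.053 and 0.100 requires three assumptions: that 17% describes patients from treatment start, that 2% to 10% are removed, and that those removed would have done worse than average (half the overall success rate at the low end, certain failure at the high end). If they would have done as well as the rest, there is no inflation. The protocol supports neither a claim that the true error rate is known to exceed 5% nor one that a large share of early failures is lost.

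It should be fixed because the protocol fixes this set expressly, the type I margin is only 0.0004, and the remedy is wording.

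**What to change.** In 12.2, 12.3.4 and the synopsis, by dated amendment:

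- Drop the 80% condition from the set that governs the final test. Define the set as all treated patients with committee-confirmed thymic carcinoma, whatever their exposure or reason for stopping. Use scans on or off treatment, and count anyone not known to be alive and progression-free at 3 months as a failure.
- Report the present 80%-drug set as a sensitivity analysis.
- Leave any stage 1 decision already taken as it stands, and report the stage 1 count in both sets.
- If the number analysed at the end is not 54, use a cut-off recalculated for that number: with stage 1 at 4/17, at least 15 successes for 55-59 patients and at least 16 for 60.
- State which population the 17% and the 33% describe.

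Merely re-admitting patients below 80% who die or progress within the first two cycles would not do. An early toxicity stop would then count if it progressed but not if it was progression-free at 3 months. A patient who stopped on day 10 and progressed at day 42 would stay out.

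No new data are needed. For patients withdrawn without progression, 11.2.1 already provides that "regular tumor imaging assessments are to be performed every 6 weeks during follow-up, until PD or until a new antitumor therapy starts". The observed rate may be lower. If 33% was meant for the present set, power with 14/54 falls to about 0.78, 0.74 or 0.67 at 2%, 5% or 10% extra failures and should be restated. As this would be a late change in an open-label trial, results in both sets should be shown.
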